### **Causality Assessment**

For this study, all AEs developing any time from administration to 7 days after discontinuation will be evaluated for relationship to study drug. For Imm 124E, the closer it is to study administration and if it recurs on rechallenge (depending on the nature of the event), it will be considered to be study drug-related.

Adverse events should be recorded as diagnoses, if available. If not, separate sign(s) and symptom(s) are recorded. One diagnosis/symptom should be entered per record.

Hospitalization will not be considered an event; however, the reason for hospitalization will be documented as an adverse event. Procedures are not events; the reasons for conducting the

procedures are. In general, only the reason for conducting the procedure will be captured as an adverse event. However, if deemed necessary by the Investigator, a procedure can be captured along with the reason for conducting the procedure.

An overdose or medication error is not an adverse event unless it is temporally associated with an unfavourable or unintended sign or symptom.

Each AE is to be classified by the Investigator as serious or non-serious. A serious adverse event (SAE) is any untoward medical occurrence or effect that occurs at any dose:

- Results in death
- Is life-threatening (i.e., an immediate risk of death)
- Requires in-patient hospitalization or prolongation of existing hospitalization
- Results in persistent or significant disability/incapacity
- Is associated with a congenital anomaly/birth defect
- Is an important medical event

An adverse event caused by an overdose or medication error is considered serious if a criterion listed in the definition above is fulfilled.

Important adverse events that may not result in death, may not be life-threatening, or do not require hospitalization may be considered serious when, based upon appropriate medical judgment, they may jeopardize the subject's safety or may require medical or surgical intervention to prevent one of the outcomes listed above.

Serious adverse events also include any other event that the Investigator or sponsor judges to be serious or which is defined as serious by the regulatory agency.

A **suspected adverse reaction** means any adverse event for which there is a reasonable possibility that the drug caused the adverse event. For the purposes of IND safety reporting, "reasonable possibility" means there is evidence to suggest a causal relationship between the drug and the adverse event. Suspected adverse reaction implies a lesser degree of certainty about causality than adverse reaction, which means any adverse event caused by a drug.

The Investigator is to report all directly observed adverse events and all adverse events spontaneously reported by the trial subject using concise medical terminology. In addition, each trial subject will be questioned about adverse events. The question asked will be "Since you began taking the study medication, have you had any health problems?"

***Procedures for Assessing, Recording, and Reporting Adverse Events and Serious Adverse Events, in Accordance with 21 CFR 312.32(a) FDA Guideline for Safety Reporting***

Throughout the duration of the study, the Investigator will closely monitor each subject for evidence of drug intolerance and for the development of clinical or laboratory evidence of adverse events. All adverse events (expected or unexpected) which occur during the course of the study, whether observed by the Investigator or by the subject, and whether or not thought to be drug-related, will be reported and followed until resolution or until they become stable.

All subjects will be under close medical supervision during their stay in the CRSU or hospital. During the entire course of the study, subjects will be encouraged to report any adverse events which may occur.

Any adverse event or other unwanted response which occurs in the course of the study should be monitored and followed up until:

- It has resolved or stabilized according to the judgment of the Principal Investigator.
- There is a return to normal or baseline values.
- It has been shown to be unrelated to the study drug.

All adverse events noted during the course of the study will be included in the final study report.

The description of the adverse event will include description of event, start date, stop date, intensity, if it was serious, relationship to test drug, change in test drug dosage, if the subject died, and if treatment was required.

Events will be coded to one of the following intensity categories below:

Toxicity Grade	Severity	Definition
1	Mild	Awareness of signs or symptoms, but no disruption of usual activity
2	Moderate	Event sufficient to affect usual activity (disturbing)
3	Severe	Event causes inability to work or perform usual activities (unacceptable)
4	Life Threatening	

Events will be coded into one of the following causality categories as defined below:

Category	Definition
Not Related	This category applies to those adverse experiences, which, after careful consideration, are clearly and incontrovertibly due to extraneous causes (disease, environment, etc.)
Unlikely	In general, this category can be considered applicable to those adverse experiences which, after careful medical consideration at the time they are evaluated, are judged to be unrelated to the test drug.
Possibly	This category applies to those adverse experiences for which, after careful medical consideration at the time they are evaluated, a connection with the test drug administration appears unlikely but cannot be ruled out with certainty.
Probably	This category applies to those adverse experiences for which, after careful medical consideration at the time they are evaluated, are felt with a high degree of certainty to be related to the test drug.
Almost Certainly	

Adverse events with the causality assessed as unrelated or unlikely are categorized as not related to study medication.

Adverse events with the causality assessed as possible or probable are categorized as related to study medication and are called adverse drug reactions.

**Any Serious Adverse Event, whether deemed drug-related or not, must be reported to the IRB, and to the Sponsor by telephone and by Fax, as soon as possible after the Investigator has become aware of its occurrence even if not all the information is available at the time of initial contact:**

**Primary Sponsor (NIAAA) [name]**

Secondary Contact (Immuron) information:

Contact person: [name], Director of Clinical Research  
Email: [[contact]](mailto:[contact])

The Investigator must complete a Serious Adverse Event (SAE) Form, and send it, via fax, to the Sponsor within 24 hours of becoming aware of the event. If the event occurs over the weekend, it will be reported on the first business day after the weekend. Accompanying documentation, such as copies of hospital case reports, autopsy report, and other documents when applicable, should be sent as soon as they are available.

Subjects who have had an SAE must be followed clinically until all parameters (including laboratory) have either returned to normal or are stabilized.

Any serious and unexpected adverse reaction (not consistent in severity, specificity, outcome or frequency, with the relevant safety information), including all deaths, must also be reported to the IRB by the Investigator according to local regulations.

## STUDY PROCEDURES AND FLOW CHART

The total expected duration of the study for each subject is up to 180 days and tabulated below:

Screening: Up to 7 days

Treatment: 28 days

Follow-ups: Day 30, day 90 and day 180 post treatment

**Table 2: Schedule of Study Procedures**

Schedule of Study Procedures	Screening	Treatment Phase		Follow-up Phase		
	Day-7 to 0	D0	D7	D30	D90	D180
Informed Consent	X					
Eligibility Criteria/Demographics	X					
Medical and Surgical History/Updated	X		X	X	X	X
Medication Record /Concomitant meds	X		X	X	X	X
Physical Exam/Vital signs	X		X	X	X	X
Anthropometric Measurements/Nutrition	X					X
Urine Pregnancy Test	X		X	X	X	
Adverse Event Assessment			X	X	X	X
Liver biopsy (if performed)	X					
Study Drug Compliance Assessment			X	X		

Assessment of Meld, DF, and Child Pugh Scores	X		X	X	X	X
Assessment of Lille Score			X			
Alcohol Addiction Advice per SOC	X		X	X	X	X
Dispense Study Drug		X				
Alcohol AUDIT and NIAAA Six Question Set	X					X
Time Line Follow Back	X					X
Tobacco/Marijuana Use Questionnaire	X					
CBC, Hepatic panel, INR, Basic metabolic panel	X		X	X	X	X
Serum-WBC-endotoxin, FACS analysis of cell types, cytokines, oxidative stress markers, soluble CD14		X	X	X		
Plasma-Metabolomics		X	X	X		
Stool 16 multi-tag pyrosequencing (microbrome), fecal calprotectin		X	X	X		
Urine-Metagenome		X				

### EXPLORATORY EVALUATIONS

The following are the analyses that might be analyzed in the serum/plasma and peripheral blood mononuclear cells (PBMC). Collected at Day 0 and Day 180.

**Table 3: Exploratory Evaluations**

Cytokines/chemokines	Serum TNF- $\alpha$ , IL-1, IL-6, IL-8, and others.
NK cells	Flow cytometry of PBMC for CD3–CD56+ cells. Cytotoxic activity will be measured by assessing intracellular perforin and granzyme expression.
Cytotoxic T cells	Flow cytometry of PBMC for CD3+CD56+ cells. Cytotoxic activity will be measured by assessing intracellular perforin and granzyme expression.
Complement activation	Plasma C3a levels and plasma circulating immune complexes

### Interpretation of Labs

All of these are continuous variables. We will compare end of treatment levels across the treatment arms correcting for baseline values. We will also compare the drop from baseline to end of treatment in these arms. We hope to demonstrate that both active arms will have lower levels of pro-inflammatory cytokines compared to those treated with steroids alone. However, no formal hypothesis testing is planned because we have no prior data to project the magnitude of change and thus cannot develop a meaningful sample size calculation. These are in many ways hypothesis generating analyses to guide future studies.

Intestinal microbiome: **These studies are exploratory and will be contingent on funding from NIAAA.** 16 S pyrosequencing is planned to describe the diversity of the microbial populations in

the stool at baseline and at end of study. There are no data on the impact of steroids or Imm-124 on the microbiome. Therefore no formal hypothesis testing is planned.

### Unscheduled Visits

An unscheduled visit may be performed at any time during the study at the subject's request or as deemed necessary by the Investigator. The date and reason for the unscheduled visit will be recorded. At the unscheduled visit, vital signs are required. All other assessments are optional and to be conducted at the discretion of the investigator.

Early discontinuation visit will occur if a subject prematurely discontinued study participation and will be similar to the Termination Visit.

## STATISTICAL METHODS PLANNED AND SAMPLE SIZE

### Determination of Sample Size

Given the potential for changes in clinical status we used a S.D. of 25% for our sample size calculations and estimated the size required to obtain 80-90% power for changes in LPS *in placebo vs. either arm* with active drug in four difference scenarios shown in **Table 4**. Due to multiple comparisons, the p value is set at 0.025.

Table 4	Scenario 1	Scenario 2	Scenario 3	Scenario 4
$\alpha$ (p value)	0.05	0.025	0.025	0.025
power (%)	90	80	90	90
placebo mean/SD drop in LPS (%)	25/10	25/25	25/25	25/25
Imm-124 E mean/SD drop in LPS at either dose (%)	50/10	50/25	70/25	50/25
N required (each group)	5	20	7	26

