## INVESTIGATIONAL PLAN

### Overall Study Design and Plan – Description

**Figure 1: Study Schema**

Subjects with severe AH (MELD score  $\geq 20$  and  $\leq 28$ ) about to receive prednisolone (40 mg/day x 28 days) will be randomized to receive either:

- Group A: 2400 mg/day Imm 124-E as 1200mg bid PO
- Group B: 4800 mg/day Imm 124-E as 2400mg bid PO
- Group C: Identical appearing placebo bid PO

Treatment will be for 28 days (**Fig. 1, above**). Given variable outcomes and response to corticosteroid therapy in patients with severe AH, a Lille model was developed by French investigators to identify subjects early in the course of treatment that are unlikely to benefit from continued treatment and in fact might have worse outcome. The Lille model takes into account patient's age, and at the start of therapy total bilirubin, albumin, creatinine, prothrombin time values and total bilirubin level on day 7 of therapy. It projects a 6-month survival probability of patients with a Lille score above 0.45 to be about 25% contrary to patients with a Lille score below this cutoff (85%). Subjects who meet the Lille criteria for failure of treatment on Day 7 or side effects requiring discontinuation of steroids will be removed from the study. Standard of care nutrition support and alcohol cessation recommendations will be provided to all subjects. Alcohol withdrawal will be managed per standard of care.

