### **Removal of Subjects from Therapy or Assessment**

Each subject will be informed of their right to withdraw from the study at any time and for any reason. Subjects may be withdrawn from treatment or assessment:

- If continuing in the study does not appear to be in the best medical interest of the subject, his/her participation may be terminated by either the Principal Investigator or the study director. Removal of an individual by the Principal Investigator will be reported to the Institutional Review Board and the appropriate regulatory agencies according to the guidelines of these groups.
- Subjects considered as treatment failure i.e. those who meet Lille criteria for failure will be removed from the study and will be offered alternative standard therapy by their treating physician.

Reasons for permanent discontinuation include the following:

- The subject decides to withdraw from the study.
- The Investigator may withdraw a subject from the study at any time if he considers that remaining in the study compromises the subject's health or the subject is not sufficiently cooperative.
- The study DSMB on behalf of NIH and the TREAT consortium may ask that a subject be withdrawn from the study if it considers that remaining in the study compromises the subject's health and after discussing the issue with the Principal Investigator.

The reasons for any subject withdrawal will be recorded on the study completion form of the case report form (CRF). The Investigator will inform the Sponsor in writing of the subject's early withdrawal for any reason.

Upon withdrawal from the study, any time after dosing has taken place, the subject will have a further hematology, serum biochemistry, urinalysis, and medical examination. Laboratory tests will be those outlined for the follow-up safety tests in Appendix 1.

If withdrawal is caused by an adverse event that the Investigator considers may be related to the Imm 124-E, it will be reported to the IRB and to the Sponsor.

Any serious unexpected adverse event which is thought to be possibly or probably related to the study drug must be reported to Sponsors by telephone within 24 hours of being informed of the SAE or on the next business day after a holiday or weekend, and then, a Serious Adverse Event form must be completed and faxed to the sponsors within 48 hours. The event must be reported to the IRB within 5 days.

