**22 subjects will be recruited to each of the three arms.**

### Other Mechanism of action related endpoints

- Intestinal permeability (stool  $\alpha$ 1 antitrypsin): Previous studies have indicated that alcoholic liver disease is associated with increased intestinal permeability. We will measure intestinal permeability, as measured by the stool  $\alpha$ 1 antitrypsin level across the two study arms correcting for baseline values using analysis of covariance. We will not plan any formal hypothesis testing because there are no prior data to guide sample size estimates etc.
- Intestinal inflammation (stool lactoferrin and calprotectin, ELISA): These are considered to be markers of intestinal inflammation. They will also be analyzed using a similar approach as noted above. We will compare the levels across both arms correcting for baseline values for these continuous variables, which we anticipate will be normally distributed.
- Systemic inflammation: We will measure the following:

A: C reactive protein

B: 4-OH nonenal and malondialdehyde (oxidative stress markers)

C: cytokines: Innate immunity- TNF- $\alpha$ , IL6, Inflammasome- IL1 $\beta$ , TH1- interferon-gamma, TH2- IL-10, IL-4, Treg-IL17, IL23 (these will be run on a multiplex machine but are subject to ongoing funding from NIAAA for these analyses).

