### **Analysis Population**

For the mechanistic endpoints, we will perform an intent-to-treat analysis. An intent to treat analysis will also be performed for the following endpoints:

- Proportion meeting Lille criteria for futility (Lille score > 0.45)
- Mortality at day 30, 90 and 180
- Change in MELD score and discriminant function adjusting at day 7 and 30 for baseline values
- Change in liver functions adjusting for baseline values on day 7 and 30.

For mechanistic and safety related endpoints, we will include an efficacy evaluable set which will only include those who have received drug for the planned duration within the study.

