### **Subject Populations**

All subjects who receive at least one dose of Imm 124-E or placebo will be included in the safety analysis while those who receive at least 7 days of treatment will be considered for the primary pathophysiology-based endpoint

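### Does recruiting 22 per arm, with no stated power and no allowance for losses, leave the endotoxin comparison short of its 80–90% power target?

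*Combined protocol and SAP*

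**What the plan says.** Determination of Sample Size sets the power range, in that the authors "estimated the size required to obtain 80-90% power for changes in LPS", and the variability: "Given the potential for changes in clinical status we used a S.D. of 25% for our sample size calculations". Table 4 lists four scenarios, with 5, 20, 7 and 26 per group. Directly below it the plan states "22 subjects will be recruited to each of the three arms". No power is attached to 22, and no dropout or non-evaluable rate appears in the documents.

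Four other places bear on how many subjects will have a late endotoxin value:

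- Overall Study Design and Plan: subjects who meet the Lille criteria "for failure of treatment on Day 7 or side effects requiring discontinuation of steroids will be removed from the study".
- Removal of Subjects from Therapy or Assessment: at withdrawal "the subject will have a further hematology, serum biochemistry, urinalysis, and medical examination". Endotoxin is not listed.
- Analysis Population: "For the mechanistic endpoints, we will perform an intent-to-treat analysis", and additionally an "efficacy evaluable set which will only include those who have received drug for the planned duration within the study". Subject Populations adds that "those who receive at least 7 days of treatment will be considered for the primary pathophysiology-based endpoint".
- Subject Disposition: missing values are not replaced by estimates, and endotoxin is compared by analysis of covariance with adjustment for baseline.

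On timing, Secondary Endpoints names Days 7 and 28, while Table 2 schedules endotoxin at D0, D7 and D30.

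**The concern.** Endotoxin is the principal secondary endpoint and the only one that sizes the trial. The chosen 22 lies between the two tabulated requirements, so its margin over the 80% figure is only two subjects per arm, and the plan does not say whether that margin is meant for losses. The larger SD protects against noisy data but not against absent samples. The protocol itself creates absences after Day 7, and the withdrawal work-up does not clearly recover them.

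If several subjects per arm had no late sample, a simple two-group comparison could fall below 80% power, and a reader could not tell from the plan whether this had been foreseen. Two further points add to the impression of a loose calculation: three descriptions of the analysis set, and a Scenario 3 entry that does not fit its own alpha.

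**Working it through.** **Inputs.** From Table 4: mean drop 25% on placebo, 50% on active (70% in Scenario 3); SD 25 (10 in Scenario 1); alpha 0.025 (0.05 in Scenario 1); power 80% in Scenario 2 and 90% in the others. Two-sided testing is taken from Safety Analysis, since Table 4 gives no sidedness.

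**Step 1: reproduce Table 4.** Normal formula per group: n = 2 (SD/difference)² (z₁₋α/₂ + z_power)².

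- Scenario 2: 2 × 1 × (2.241 + 0.842)² = 19.01, so 20. Stated 20.
- Scenario 4: 2 × 1 × (2.241 + 1.282)² = 24.82, so 25. Stated 26.
- Scenario 1: 2 × (10/25)² × (1.960 + 1.282)² = 3.36, so 4. Stated 5.
- Scenario 3: 2 × (25/45)² × (2.241 + 1.282)² = 7.66, so 8. Stated 7.

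The noncentral t gives 5, 21, 10 and 27 for Scenarios 1 to 4. Scenarios 2 and 4, which bracket the chosen size, therefore fit an unadjusted two-sided test at 0.025 to within one subject. Scenario 3 is one short by the normal formula and three short by the t-test. At 7 per group its power is 87.0% (normal) or 77.8% (t). The stated 7 is what the normal formula gives at two-sided 0.05 or one-sided 0.025.

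**Step 2: power at 22 and below, unadjusted.** Standardised difference 25/25 = 1, noncentrality √(n/2), two-sided alpha 0.025.

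| Evaluable per arm | Loss from 22 | t | Normal |
|---|---|---|---|
| 22 | 0% | 83.5% | 85.9% |
| 21 | 5% | 81.5% | 84.1% |
| 20 | 9% | 79.3% | 82.1% |
| 19 | 14% | 76.8% | 79.98% |
| 17 | 23% | 71.2% | 75.0% |
| 13 | 41% | 56.9% | 62.1% |

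The first failing loss is thus 9% on the t-test and 14% on the normal formula.

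**Step 3: with the planned baseline adjustment.** Table 4's SD is for the drop in LPS. If r is the correlation between baseline and that drop, the residual SD is 25√(1 − r²), and one degree of freedom is lost. The documents give no r. At an assumed r = 0.5, power (t / normal) is 92.9/94.4% at 22, 90.1/92.1% at 20, 83.8/87.0% at 17 and 70.6/75.9% at 13. The smallest arm holding 80% is 16 (81.1%, t) or 15 (82.1%, normal), a tolerated loss of 27% or 32%. With r near zero the result returns to Step 2.

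**Step 4: the SD.** Subject Disposition reports an SD of 8–10% for LPS levels in prior studies. That is for levels, not explicitly for the drop, so it cannot simply replace 25. If the SD of the drop were 10, then 5 per arm would give 85.6% power (t) at alpha 0.025.

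**The case for a change.** The strongest case for a change is that the loss is built into the protocol. Lille failures are removed by rule at Day 7, nothing is imputed, and the set defined by planned treatment duration excludes every removed subject. On the unadjusted calculation that Table 4 appears to use, two or three missing subjects per arm bring power to about 80% or just under. The two-subject margin may be an informal 10% uplift (20 × 1.10 = 22), but the plan does not say so, and a proper 10% allowance would be 20/0.90 = 22.2, hence 23.

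It stands that the power at 22 and the expected evaluable number are unstated and would have been worth a sentence. It does not follow that the design is short. The exact power at 22 can be bracketed from Table 4 itself. A shortfall needs an assumed loss rate together with the assumption that baseline adjustment gains little, and the documents support neither. The Day 7 comparison, one of the two named time points, is largely untouched by removals made at Day 7.

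Removal that depends on response could also bias a late comparison. That is a question of interpretation; quoting a power figure would not cure it.

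**Conclusion.** No change to the plan follows. With all 22 per arm evaluable, power per dose is about 84–86% unadjusted (difference 25, SD 25, two-sided alpha 0.025), within the stated 80–90%. Whether it stays there at the end of treatment depends on a loss rate and a baseline correlation that the documents do not give. Across the assumed range, the first failing loss is 9–14% with no adjustment, while losses of 27–32% are tolerated at r = 0.5.

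Stating these figures would make the document clearer but would alter neither recruitment nor any analysis. The other loose ends are details that analysts can settle sensibly. Table 2 has only one endotoxin draw after Day 7, so the Day 28 value must be the D30 sample. Intent-to-treat is named for the mechanistic endpoints, with the planned-duration set as an addition, and the number analysed at each time point can be reported by arm. The Scenario 3 entry is at most a slip in an illustrative column that played no part in choosing 22. The primary endpoint, safety, is unaffected.
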